4.3.7. Subgroup Analyses for Primary Endpoint

Summaries with descriptive statistics and frequency counts on the primary efficacy endpoint for both groups will be provided for the subgroups indicated below. Forest plots will also be created for subgroup analyses and will display treatment differences. The subgroups will be:

- Gender (female vs. male)
- Age Group (12 months to 23 months; 2 to 11 years; 12 to 17 years; 18 to 64 years; and 65 years and above)
- Country/Region (US, China, EU, ROW)

•

- Concomitantly taking everolimus (yes vs. no)
- Concomitantly taking cannabidiol (yes vs. no)
- mTOR medication (taking sirolimus, everolimus, tacrolimus vs. no)

4.3.8. Handling of Missing Data

Available data from patients who withdraw from the study prematurely will be included in analyses, unless otherwise indicated. Summary statistics will be reported based upon observed data. No data will be imputed or carried forward for missing values or for patients who discontinue early. All missing data and missing or partial dates for AEs and medications will be queried for a value. In the unlikely event that no value can be obtained, substitutions will be made as described below.

• Missing and Partial Start/Stop Dates - AEs and Concomitant Medications

The handling of partial start and stop dates for AEs are described in Table 3 below. Similar algorithms for handling missing and partial dates of concomitant medication usage are described in Table 4. In both cases, if a stop date is complete and an imputed start date is after the stop date, the start date will be set to the stop date.

• Missing Seizure/Medication Diary Entries

The calculation of seizure frequency endpoints will include only days for which diary entries are available. Missing seizure data will not be imputed.

Table 3: Adverse Event Start/Stop Date Imputation

Parameter	Missing	Additional Conditions	Imputation
Start date for AEs		M and Y same as M and Y of first dose of IP	Date of first dose of IP
		Y same but M prior to month of first dose of IP	Last day of month
	D	Y same but M after month of first dose of IP	First day of month
		Y is prior to year of first dose of IP	Last day of month
		Y is after year of first dose of IP	First day of month
		Y is same as Y of first dose of IP	Month of first dose of IP
	M	Y is prior to year of first dose of IP	M = December
		Y is after Y of first dose of IP	M = January
		Y same as Y of first dose of IP	Date of first dose of treatment
	D and M	Y prior to Y of first dose of IP	M and D will be December 31
		Y after Y of first dose of IP	M and D will be January 1
	Y, or M, D, Y	Y and/or start date missing	Date of first dose of treatment
Stop date for AEs	D	M and Y not missing	Use last day of month (i.e. D may take on values of 28, 29, 30, or 31, depending on month)
	M	Y not missing; if D also missing, impute D as described above	M = December
	Y, or M, D, Y	Y and/or stop date missing.	No imputation. Date left missing.

D=day, M=month, Y=year

Note: In all cases, if an estimated start date is after a complete stop date, the start date will be set to the AE stop date. Similarly, if the estimated stop date is before a complete or imputed start date, use the last day of the start day month.

Table 4: Imputation for Prior/Concomitant Medication Missing and Partial Dates

Parameter	Missing	Additional Conditions	Imputation
	D only	M and Y are not missing or imputed.	Use 1st day of M.
	M only	D and Y are not missing or imputed.	M = January
	M and D	Y is not missing or imputed.	Use Jan 01 of Y
Start date for con meds			
	M, D, and Y	None - date completely missing	No imputation but considered concomitant unless stop date is prior to first dose of IP.
	D only	M and Y are not missing or imputed.	Last day of month
	M only	D and Y are not missing or imputed.	M = December
Stop date for con meds	M and D	Y is not missing or imputed	Use Dec 31 of Y
	M, D, and Y	None - date completely missing and NOT ongoing	No imputation

Note: In all cases, if an estimated start date is after a complete stop date, the start date will be set to the end date of medication.

5. BASELINE, DISPOSITION, AND EXPOSURE

5.1. Study Day and Analysis Window

For reporting purposes, Study Day will be calculated from the date of the Baseline Treatment Visit (Visit 2, Day 1). Similarly, Study Week will be calculated from the date of the Baseline Treatment Visit.

For all assessments performed on or after the first day of treatment, i.e. reference date \geq date of first dose of IP, Study Day is calculated as:

• Study Day = (date of assessments/events - first day of treatment) + 1

For assessments performed prior to the first day of treatment, i.e. reference date < date of first dose of IP, Study Day is calculated as:

• Study Day = date of assessment/event – first day of treatment.

5.2. Definition of Baseline

The Baseline Visit is defined as Visit 2 (Day 1). Baseline values for non-seizure efficacy and safety assessments will be the last values collected prior to the first administration of IP (i.e., GNX), unless otherwise specified.

Baseline seizure frequency data is collected during the four weeks between the Screening Visit (Visit 1, Week -4) and the Baseline Visit (Visit 2, Day 1). This interval may range from no less than 28 days to no more than 34 days.

5.4. Demographics and Baseline Characteristics

Demographics and baseline characteristics will be summarized and listed for all patients in the Safety Population. Demographic characteristics, including age, height, weight, and BMI, will be summarized with descriptive statistics (n, mean, median, SD, minimum and maximum). Categorical characteristics such as age group (\leq 17 years, > 17 years), weight group (\leq 28 kg, > 28 kg), sex, race and ethnicity, will be summarized as counts and percentages.

Additionally, baseline clinical characteristics including results of genetic testing for pathogenic or likely pathogenic TSC1 or TSC2 variant, Tanner Staging, number of AEDs taken and stopped prior to screening, neurological exam results, developmental examination results (pediatric patients aged 2 to 17, inclusive), and Seizure Identification and Diagnostic Review Form (SIF/DRF) responses including baseline seizure types reported as primary and non-primary, IQ, intellectual disabilities, and EEG findings will be summarized.

Baseline values of efficacy and safety parameters will be summarized in the respective analysis tables.

5.5. Subject Disposition

The number of patients screened for this study, the number of screen failures and the number of patients who received at least one dose of IP will be summarized. Reasons for screen failure will be provided in the data listing. The final disposition of all patients who receive IP will be summarized. Reasons for discontinuation of study treatment and for discontinuation of study participation will be summarized. The total number and percentage of patients who complete the study will be summarized.

A listing of patient disposition will be provided. In addition, a summary of the number of patients included in each analysis set will be presented.

5.6. Eligibility Criteria and Protocol Deviations

The clinical team will review and identify deviations and the deviations will be recorded into the database. A data listing of subjects who violate any of the inclusion/exclusion characteristics will be provided as well as a data listing of subjects with other protocol violations.

5.7. Prior and Concomitant Medications

All investigator terms for medications recorded on the CRF will be coded using the World Health Organization Drug Dictionary Enhanced (WHODDE) Anatomical Therapeutic Chemical (ATC) drug dictionary. The number (percentage) of subjects who took prior and concomitant medications will be summarized in the Safety population by Anatomic Therapeutic Chemical (ATC) classification level 2 and Preferred Term (PT).

Prior medications are defined as medications/therapies that started and stopped prior to the first dose of study drug. Concomitant medications are defined as medications (other than the study drug) administered on or after the first dose of the study, regardless of when the medications started.

The number and percentage of patients in the Safety population reporting use of prior and concomitant treatments will be summarized and listed separately. In addition, antiepileptic prior and concomitant drugs (AEDs) and rescue medications will be presented separately.

5.8. Medical History

Medical history will be coded using Medical Dictionary for Regulatory Activities (MedDRA), version 25.1. The number and percent of subjects with clinically significant medical history at screening will be summarized by system organ class (SOC) and preferred term (PT) in the Safety population. Medical history will also be listed.

5.9. Study Drug Exposure

Exposure to study medication (GNX) will be summarized as the number of days on treatment, percentage of days dosed, maximum daily dose received, and total dosage received. The denominator for the percentage of days of study drug is the number of days the patient is on treatment in the respective part of the study. If the patient stops taking IP during the study, the last day that drug was taken will be used as the last day of treatment. For patients who are ongoing at the end of a specific part of the study, the last known treatment date will be used for the last day on treatment.

A listing of exposure data for each patient including total daily dose, start and end dates, and reason for any dose change will also be provided.

5.10. Study Drug Compliance

The percent compliance with study drug will be estimated using dosing information as follows:

 $\frac{[total\ doseage\ during\ maintenance\ period]}{[(last\ day\ of\ maintenance\ period)-(first\ day\ of\ maintenance\ period)+1]\times(target\ daily\ dose)}\ x100$

Reported dosing by visit and calculated compliance values will be listed.

5.11. Cross-Over Titration Summary

The end date of Double-Blind Maintenance Period and the start date of Cross-over Titration period are supposed to be two different days. However, one overlapped day may exist in some rare scenarios. When this appears in the EDC data, the following rule will be implemented to handle the analysis and data summary:

- 1. The last visit date in DB maintenance period will not be changed. This date will be set as the end date of the DB phase.
- 2. All scheduled/unscheduled tests (Lab, Vital Sign, ECG etc.) have been done on the last visit date in DB maintenance period will be summarized in the DB phase.
- 3. All the TEAEs, CMs and seizures occurred on the last visit date in DB maintenance period will also be summarized in the DB phase.

The following safety endpoints will be summarized descriptively:

- Incidence and severity of AEs, SAEs, and withdrawals and dose-reductions due to AEs
- Physical/neurological/developmental examinations
- Vital sign measurements
- 12-lead ECGs
- Clinical laboratory tests
- Suicidal ideation and behavior risk monitoring

For TEAEs presented by relationship to study drug, the closest relationship to study drug for each event during the clinical trial will be presented for each subject. If the relationship to investigational product is missing for a TEAE, a causality of "Related" will be assigned. The imputed values for relationship assessment will be used for incidence summaries, while the actual values will be presented in data listings.

All AEs, SAEs, TEAEs leading to study drug interruption, TEAE leading to study discontinuation, SAEs leading to death and Grade 4 or higher AEs will be displayed in separate listings.

6.2. Clinical Laboratory Evaluations

Laboratory data collected in this study include serum chemistry, hematology values and urinalysis results. The baseline laboratory value is defined as the last value observed prior to the first administration of study drug. Any values collected after the administration of study drug are regarded as post-baseline. Change from baseline will be calculated as the post-baseline value minus the baseline value. Only the numeric part in laboratory values that contain non-numeric qualifiers, such as less than (<) a certain value or greater than (>) a certain value, will be used in the summary statistics.

Laboratory values and change from baseline in these values will be listed and summarized for patients in the Safety Population by group (chemistry, hematology or urinalysis) and by visit. Listings of patients with positive drug screen or pregnancy results will be provided.

Descriptive summaries of continuous laboratory values and change from baseline in these values will include the number of observations, mean, SD, median, minimum and maximum values at each time point. Data will be summarized in SI units. Shift tables comparing baseline classification based on reference range (i.e., normal, low, or high) to the worst classification recorded post-baseline will be presented. In the case that a patient has both "low" and "high" post-baseline results for the same laboratory parameter, the patient will be counted under both "low" and "high". A patient will be counted under the "normal" category post-baseline only if all post-baseline results are categorized as "normal".

For non-numeric urinalysis data, a shift table comparing baseline results (negative, trace or positive) to the maximum post-baseline result will be presented.

Listings of laboratory results for each patient will be presented. Values outside of the laboratory's reference range will be flagged in the listing. A by-patient listing of laboratory values outside the normal reference range for the parameter will be produced.

Developmental examinations will be conducted on pediatric patients 2 to 17 years of age, inclusive. Developmental parameters assessed include speech and language skills, motor skills and social skills. The number and percentage of pediatric patients will be summarized by each parameter.

6.4. Electrocardiogram (ECG)

Safety ECG measurements will be collected throughout the study. Baseline ECG values are those collected at Visit 2 (Day 1) prior to the first dose of IP.

ECG parameters include heart rate, PR interval, RR interval, QRS interval, QT (uncorrected) interval, QTcF interval, and QTcB interval. In addition, the overall interpretation of the investigator will be documented as normal, abnormal but not clinically significant (NCS), or abnormal and clinically significant (CS). All clinically significant abnormal findings will be reported as AEs also. Absolute values and change from baseline in post-baseline values will be summarized. By-patient listings of ECG data and overall interpretations will be provided.

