8.3.3 Electrocardiograms

12-lead ECGs will be performed to collect the electrical activity of the heart throughout the study to monitor safety. An evaluation of “normal” by a physician must be obtained before the participant is enrolled in the study.

12-lead ECGs will be obtained as outlined in the SOA (see [Section 1.3](#)) using an ECG machine that automatically calculates the HR and measures PR, QRS, QT, and QTc intervals.

12-lead ECGs will be performed at Visit 1 (screening), Visit 2 (baseline), Visit 4 (Week 1), and Visit 8 (Week 5), and Visit 12 (Week 16).

Participants who continue in the OLE will also have 12-lead ECGs conducted at Visit 15 (Week 18) and Visit 17 (Week 20).

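### SAP 6.4 gives ECG change from baseline no fallback to the screening ECG, and leaves abnormalities not judged clinically significant without a count by arm

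*SAP*

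**What the plan says.** **Baseline.** SAP 6.4 states: "Baseline ECG values are those collected at Visit 2 (Day 1) prior to the first dose of IP". The general rule in SAP 5.2 is wider, but it gives way to a specific rule elsewhere: "safety assessments will be the last values collected prior to the first administration of IP (i.e., GNX), unless otherwise specified". Protocol 8.3.3 and the Schedule of Activities place 12-lead ECGs at Visits 1, 2, 4, 8 and 12, so two pre-dose ECGs are planned for every participant. Protocol 8.3.3 also asks that an ECG evaluation of normal "by a physician must be obtained before the participant is enrolled in the study".

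**Display.** SAP 6.4 names heart rate and the PR, RR, QRS, QT, QTcF and QTcB intervals, and a three-level overall interpretation by the investigator: normal, abnormal not clinically significant (NCS), or abnormal clinically significant (CS). On summaries it says: "Absolute values and change from baseline in post-baseline values will be summarized". The interpretation appears only in the sentence on listings: "By-patient listings of ECG data and overall interpretations will be provided". On the most serious category it adds: "All clinically significant abnormal findings will be reported as AEs also".

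**The concern.** There are two separate gaps, both in a safety display.

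First, where SAP 6.4 and SAP 5.2 differ, 6.4 governs. Read literally, a missing or post-dose Visit 2 ECG leaves the participant with no baseline and no change value at any later visit, even though a screening ECG was recorded. Collected data go unused for no stated reason.

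Second, 12-lead ECG is a named safety measure among the endpoints of both documents, yet the only ECG summary promised is of continuous values. A participant who moves from normal to NCS on treatment, or whose QTc rises markedly without being judged CS, appears in a listing but in no count by arm. Because the protocol asks for a normal evaluation before enrolment, a by-arm count of later abnormal interpretations would come close to a treatment-emergent measure, and the fields for it are already recorded.

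**Working it through.** The documents give no ECG figure to reproduce, so the check is a comparison of sections plus one piece of arithmetic on an assumed rate.

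**1. How the SAP treats comparable safety data**

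| Data | Baseline | Categorical result |
|---|---|---|
| Laboratory (SAP 6.2) | last value before first dose | shift table, baseline to worst post-baseline |
| Vital signs (SAP 6.3) | last assessment before first dose, Visit 2 being only the typical case | overall interpretation listed |
| Physical examination (SAP 6.3) | not separately defined | same three-level scale; abnormal changes given as counts and percentages |
| Neurological examination (SAP 6.3) | not separately defined | same three-level scale; number and percentage abnormal |
| ECG (SAP 6.4) | Visit 2 pre-dose, no fallback | overall interpretation listed |

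ECG is the only row with a fixed-visit baseline. On categorical display it matches vital signs and differs from the other three.

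**2. Where each kind of ECG abnormality is counted**

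- CS: reported as an adverse event (SAP 6.4) and so counted, if treatment-emergent, by system organ class and preferred term (SAP 6.1).
- NCS: Protocol 8.4.5 says a move from a normal to an abnormal value can be an adverse event. It then leaves the investigator to decide whether the change is clinically significant and for that reason an adverse event. A finding marked NCS need not enter the adverse event tables, and SAP 6.4 provides no other count.
- QTc outlier not judged CS: SAP 4.1 gives n, mean, SD, median, minimum and maximum. The maximum shows that an extreme occurred and how large it was. It does not show how many participants had one.

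**3. Participants who would lose change data**

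Inputs: 128 planned participants (SAP 3.2); proportion *m* without a valid pre-dose Visit 2 ECG, assumed because neither document gives it. Number affected = 128 × *m*.

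- *m* = 2%: 128 × 0.02 = 2.56, about 3
- *m* = 5%: 128 × 0.05 = 6.4, about 6
- *m* = 10%: 128 × 0.10 = 12.8, about 13

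Absolute post-baseline values for these participants would still be summarised; only the changes are lost.

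**The case against.** The case for leaving 6.4 alone has real weight.

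- **The important findings are already counted.** This stands for CS abnormalities, which reach the adverse event tables. A reader might infer that new ECG abnormalities in general are visible only through averages. The documents do not support that: there is the adverse event route, SAP 4.1 requires the minimum and maximum, and every interpretation is listed by patient. The gap is confined to NCS findings and to outliers not judged CS.
- **ECG is not the only such case.** This also stands: vital-sign interpretations are listed without a count too. But physical and neurological findings on the identical scale are counted, and no reason is given for the difference.
- **SAP 4.1 already prescribes counts and percentages for categorical variables.** That rule governs how a categorical variable is shown when it is summarised. SAP 6.4 does not say the interpretation will be summarised. At best the text is ambiguous.
- **The baseline point may touch almost nobody.** The Visit 2 ECG is scheduled for all, and Protocol 8.1.2 starts treatment after the Visit 2 assessment, so a post-dose ECG at that visit would depart from the protocol. For anyone with a pre-dose Visit 2 ECG, 5.2 and 6.4 normally give the same baseline. SAP 6.4 also does not use the word only. The number is indeed unknown and may be small. Missing ECGs are nevertheless plausible: Protocol Section 8 allows remote assessments, and the travelling-nurse tasks it names do not include an ECG. The literal text offers no fallback.

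A reader might also want to show statistically that an effect on a few participants would be missed. The documents cannot carry that argument: they give no variability for ECG changes and plan no between-arm test of them. Nor would it support a table of interpretations, since nothing ties a given interval change to an interpretation category.

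**Conclusion.** The point holds as a minor improvement to a safety display. SAP 6.4 sets an ECG baseline with no fallback. It overrides SAP 5.2, differs from the laboratory and vital-sign rules, and drops change data that the Visit 1 ECG could supply. The size is unknown: about 3 to 13 of 128 if 2% to 10% lack a valid pre-dose Visit 2 ECG, and that range is an assumption. Separately, treatment-emergent NCS abnormalities and QTc outliers not judged CS are in no by-arm count, unlike physical and neurological findings on the same scale. This second part rests on reading 6.4 as committing to no more than it says about the interpretation. Neither part affects the efficacy analyses, the type I error or the sample size.

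**What to change.** In SAP 6.4:

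1. Define ECG baseline as the last ECG before the first dose of IP, whether from Visit 1 or Visit 2, in line with SAP 5.2.
2. Add a by-arm shift table of overall interpretation (normal, NCS, CS) from baseline to the worst post-baseline result up to Visit 12, with counts and percentages. Stopping at Visit 12 keeps the arms distinct, because participants entering the extension are then cross-titrated so that all receive GNX.
3. Add by-arm counts of participants exceeding QTcF value and change limits that the sponsor states in advance.

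The cost is a few sentences and one or two descriptive tables from fields already recorded, with no new data collection. One trade-off should be noted in the text: a Visit 1 baseline is older than a Visit 2 one, by the 28 to 34 days that SAP 5.2 allows between the visits. A footnote giving the number of participants who used it would be enough.

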6.5. Columbia-Suicide Severity Rating Scale (C-SSRS)

The Columbia-Suicide Severity Rating Scale (C-SSRS) is a patient questionnaire that evaluates suicidal ideation and behaviors. The results (yes/no) from the 5 questions under suicidal ideation and the 5 questions under suicidal behavior will be summarized at baseline and post baseline using percentages and counts. The denominator for percentages will be the number of subjects with a C-SSRS assessment at baseline or at any time post baseline. The post-baseline by-question summary will list a subject as "yes" if they selected yes at any time after baseline.

The C-SSRS suicidal behavior and suicidal ideation scores recorded at baseline and any changes in post-baseline scores from the previous visit will be summarized descriptively by visit, including the number and percentage of subjects reporting any suicidal behavior and any suicidal ideation as defined in Table 5. Adult and pediatric C-SSRS data will be summarized separately.

C-SSRS data collected, including scores for suicidal ideation, intensity of ideation and actual suicide attempts, will be listed by patient and visit.

Table 5: C-SSRS Categories for Analysis

Category	C-SSRS Item response is "YES"
Suicidal behavior	Preparatory acts or behavior
	Aborted attempt
	Interrupted attempt
	Actual attempt
	Complete suicide
Suicidal ideation	Wish to be dead
	Non-specific active suicidal thoughts
	Active suicidal ideation with any methods (not plan) without intent to act
	Active suicidal ideation with some intent to act, without specific plan
	Active suicidal ideation with specific plan and intent
Non-suicidal self-injurious behavior	Non-suicidal self-injurious behavior

